In Iraq, mental health services incorporation into oncology care remains substantially inadequate. Mental health professionals are scarce in most oncology centers, and psychological screening is not routinely performed during cancer diagnosis or follow-up. Cultural stigma surrounding mental illness may also contribute to the underreporting of emotional symptoms and poor help-seeking behavior. According to a 2023 WHO-EMRO report, less than 15% of patients in Iraq received psychological support, even though studies consistently demonstrate a high rate of undiagnosed mood disorders in this group of patients (12).

The present study aims to examine the psychosocial, clinical, and economic correlations of depression, anxiety, and stress among breast cancer patients in Al-Anbar city. Applying a multidimensional analytic approach, including multivariate linear and logistic regression, ROC analysis, and path modeling. This study explains how individual, emotional, and treatment-related factors interact to shape mental health outcomes. The findings are intended to guide more culturally sensitive and systemically integrated psychological interventions for cancer patients in Iraq and the region.

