## **2-Materials and Methods**

### **2-1 Study design**

This is a cross-sectional observational study that was conducted between January and May 2025 in Al-Anbar Oncology Centre, Al-Anbar, Iraq.

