### **2-2 Study population and sampling technique**

The study population consisted of all patients diagnosed with breast cancer who attended the Al-Anbar Oncology Centre in Al-Anbar, Iraq, between January 5th and May 30th, 2025.. Patients diagnosed with breast cancer at any stage and who provided informed consent to participate were included in the study.

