### **2-3 Sample Size Calculation**

The sample size was calculated using the standard formula for cross-sectional studies, with the following parameters: a 95% confidence level, a 5% margin of error, and an expected prevalence of psychological distress of 50% to yield the largest possible sample size. Based on these assumptions, the minimum required sample size was estimated to be 384 participants. To enhance the statistical power and compensate for potential non-response or incomplete data, a larger sample was targeted. Consequently, a total of 500 breast cancer patients were enrolled in the final analysis, exceeding the minimum requirement.

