## **2-6 Data Analysis**

Data was analyzed using IBM SPSS Statistics version 26. Descriptive statistics (mean, standard deviation, frequency, and percentage) were used to summarize demographic and clinical variables. The Kolmogorov-Smirnov test was applied to assess the normality of continuous variables, and due to non-normal distribution, non-parametric tests were used.

Bivariate analyses included Spearman's correlation coefficient to evaluate associations between psychological outcomes (depression, anxiety, stress) and continuous predictors such as sleep quality, cost, and number of children. The Kruskal-Wallis H test was employed to examine differences in distress levels across cancer stages.

Categorical associations were evaluated using Pearson's Chi-square test. Binary logistic regression analysis was conducted to identify predictors of severe anxiety. Additionally, multivariate linear regression models were constructed for each psychological outcome (PHQ-9, GAD-7, stress), and multicollinearity was assessed using the Variance Inflation Factor(VIF).

Receiver Operating Characteristic (ROC) curve analysis was used to assess the predictive accuracy of stress scores for severe anxiety, with Area Under the Curve (AUC) interpreted based on conventional thresholds. Conceptual path modeling was used to explore potential indirect relationships between stress and anxiety, mediated by sleep disturbance and impaired daily performance.

All tests were two-tailed, and a p-value of less than 0.05 was considered statistically significant.

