**Table 5:** Binary Logistic Regression – Predicting Severe Anxiety

Predictor	Odds Ratio (OR)	95% CI	P-value
Depression (PHQ-9)	1.32	1.18 – 1.56	<0.001

Anger	1.27	1.11 – 1.49	0.002
Stress Level	1.14	1.03 – 1.35	0.017
Psychological Support	0.54	0.33 – 0.91	0.021
Cancer Stage	0.61	0.33 – 0.87	0.049

[figure not shown]
Binary logistic regression (**Table 5**) showed that depression, anger, and stress significantly increased the odds of severe anxiety, while psychological support and advanced cancer stage were protective. The corrected model (**Table 6**) confirmed these associations.

**Table 6.** Logistic Regression Predicting Severe Anxiety (Corrected Model)

Predictor	Coef. ( $\beta$ )	Std. Error	z-value	p-value	95% CI (Lower – Upper)
PHQ9_Total	0.42	0.06	6.92	<0.001	0.30 – 0.53
Anger	2.08	0.48	4.36	<0.001	1.14 – 3.02
Psych Support	-0.18	0.34	-0.52	0.606	-0.84 – 0.49
Cancer Stage	0.92	0.29	3.20	0.0014	0.36 – 1.48

[figure not shown]
This table presents the corrected logistic regression model for predicting severe anxiety. PHQ9\_Total and anger were significant positive predictors, while psychological support did not show a significant protective effect in the adjusted model.

**Figure 2.** ROC Curve for stress predicting severe anxiety.

The ROC curve (**Figure 2**) illustrates the predictive value of stress scores for severe anxiety, with an AUC of 0.74 ( $p < 0.001$ ), indicating fair discriminative accuracy.

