Furthermore, Kruskal-Wallis analysis confirmed significant differences in mean ranks of depression, anxiety, and stress across cancer stages ( $H = 14.76$  to  $31.09$ ,  $p < 0.01$ ). These findings are supported by evidence from Iran and neighboring countries, where patients with stage III and IV breast cancer reported higher rates of emotional distress compared to the early stages of the disease (14). The increased psychological vulnerability in advanced stages underscores the need for stage-specific psychosocial interventions in cancer care protocols

Interestingly, total treatment cost showed a weak but statistically significant inverse correlation with psychological distress variables (e.g., PHQ-9\_Total:  $r = -0.11$ ,  $p = 0.017$ ). Although initially counterintuitive, this finding may reflect a perceived sense of security or access to higher-quality care among patients with greater financial capacity. Similar interpretations were reported in recent findings from Turkey, where patients with access to private sector services and higher financial resources exhibited lower levels of psychological distress despite elevated treatment costs, suggesting that financial ability may buffer emotional burden through enhanced control and perceived care quality (17).

As for psychological support, logistic regression models from this study suggested a protective effect ( $OR = 0.54$ ), though this was not statistically significant in the adjusted model ( $p = 0.606$ ). The lack of significance may be attributed to limited availability or underutilization of structured psychological services in the region, a challenge frequently reported in Iraq and across low-resource Middle Eastern settings. (18,19). Nonetheless, the direction of effect emphasizes the urgent need to integrate psychosocial support into routine oncology care.

Among all predictors examined, depression (PHQ9\_Total) and anger emerged as the strongest independent predictors of severe anxiety in both logistic and linear regression models ( $\beta = 0.42$  and  $2.08$ , respectively,  $p < 0.001$ ). These findings support prior research indicating that depressive symptomatology often precedes or co-occurs with anxiety in cancer patients, especially when emotional regulation is compromised (11)

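### The Discussion argues for routine psychosocial support from the direction of a null estimate, pairs that estimate's p-value with another model's odds ratio, and the design cannot identify an effect of support

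*Combined protocol and SAP*

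**What the plan says.** Section 2-1 states: "This is a cross-sectional observational study that was conducted between January and May 2025". Section 2-2 admits consenting patients with breast cancer at any stage and describes no allocation to support. Section 2-4 describes the PHQ-9 and GAD-7 but does not define psychological support: not its type, its timing or its provider. Section 2-6 plans a binary logistic regression for severe anxiety, gives no covariate list, and sets two-sided significance at 0.05.

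Section 3 reports two logistic models for severe anxiety.

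- Table 5 contains PHQ-9, anger, stress, support and stage. Support has OR 0.54, 95% CI 0.33 to 0.91, p = 0.021.
- Table 6, labelled as the corrected model, contains PHQ-9, anger, support and stage. Support has coefficient -0.18, SE 0.34, p = 0.606, 95% CI -0.84 to 0.49. The text under it says that "psychological support did not show a significant protective effect in the adjusted model".

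The Discussion calls OR 0.54 protective, notes p = 0.606, attributes the lack of significance to limited availability or underuse of services, and concludes: "Nonetheless, the direction of effect emphasizes the urgent need to integrate psychosocial support into routine oncology care". Its closing paragraph on the path model takes a weak inverse association of support with anxiety (r = -0.07) as a sign that stronger emotional resources might cushion the passage from stress to anxiety.

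On who receives support, the Introduction describes scarce professionals, no routine screening, stigma and poor help-seeking, and cites a report that "less than 15% of patients in Iraq received psychological support".

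**The concern.** There are three linked problems.

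1. **Mixed sources.** The Discussion puts the effect size of one model beside the p-value of another. A reader takes away a near-halving of the odds that narrowly lacked support from the data, when the corrected model shows a much smaller and very imprecise association.

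2. **Inference from direction.** A care recommendation is drawn from the sign of an estimate that is compatible with sizeable benefit and sizeable harm. Limited availability could explain poor precision, but it does not turn the sign into evidence.

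3. **No identified effect.** Support was received, not assigned, and the comparison group may mix patients who did not need it with patients who could not get it. Depression and anger enter both models, and no second time point is described. If distress prompts support, they are confounders. If support lowers distress, they lie on its pathway and adjustment removes that part of any benefit. One concurrent measure cannot separate the two, so the bias has unknown sign.

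At stake is whether readers conclude that this study shows support to be effective.

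**Working it through.** **Table 6, reproduced.** Inputs: coefficient -0.18, SE 0.34.

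- z = -0.18 / 0.34 = -0.53, two-sided p about 0.60. Stated: -0.52 and 0.606. A coefficient of -0.175 before rounding gives z = -0.515, p = 0.607 and CI -0.84 to 0.49, so the row agrees within rounding.
- OR = exp(-0.18) = 0.84.
- 95% CI = exp(-0.18 ± 1.96 × 0.34) = 0.43 to 1.63: from 57% lower to 63% higher odds.

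**Table 5, reproduced.** ln(0.54) = -0.616. SE from the interval = [ln(0.91) - ln(0.33)] / 3.92 = 0.259. z = -2.38, p about 0.017 against 0.021 stated, which is roughly consistent. So 0.54 belongs with p = 0.021, and p = 0.606 belongs with 0.84.

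**The correlation.** If r = -0.07 is a simple correlation on N = 500, t = -0.07 × √(498 / (1 - 0.0049)) = -1.57, p about 0.12. By Fisher's transformation the 95% CI is -0.16 to 0.02. It is compatible with zero.

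**How far PHQ-9 alone could move the odds ratio (illustration).** Inputs from the documents: PHQ-9 SD 6.11 (Table 1) and 0.42 log-odds per PHQ-9 point (Table 6). Assumptions: PHQ-9 is normal, anger is ignored, severe anxiety has a prevalence of 20-40% (the documents do not give it), and the groups differ by 1 to 3 points.

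Odds ratios are non-collapsible, so exp(0.42 × points) does not give the change between a model with PHQ-9 and one without it. Instead:

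- P(severe | PHQ-9) = expit[a + 0.42 × (PHQ-9 - mean)], with a solved so that the average over PHQ-9 equals the assumed prevalence.
- Shift PHQ-9 by d points, average again, and take the ratio of the two marginal odds.

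| Prevalence | d = -1 | -2 | -3 | +1 | +2 | +3 |
|---|---|---|---|---|---|---|
| 20% | 0.79 | 0.62 | 0.48 | 1.26 | 1.58 | 1.98 |
| 30% | 0.80 | 0.63 | 0.50 | 1.25 | 1.55 | 1.93 |
| 40% | 0.80 | 0.64 | 0.51 | 1.24 | 1.54 | 1.92 |

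In round figures this is 0.80, 0.63 and 0.50 downward, and 1.25, 1.55 and 1.95 upward. The reported 0.84 is a factor of 1.20 (1 / 0.835) away from no effect, so even a one-point difference exceeds it.

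- If support lowers PHQ-9 by 1 to 3 points, conditioning on PHQ-9 hides a benefit of about 0.80 to 0.50.
- If recipients score 1 to 3 points higher for other reasons, leaving PHQ-9 out inflates the OR by about 1.25 to 1.95. If they score lower, it deflates the OR by the first set of factors.

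**Cross-check by simulation (assumed inputs, Table 6 coefficients for PHQ-9 and anger).** When support acts only through PHQ-9 and anger, with no selection and a 2 to 3 point benefit, the OR is 0.60 to 0.47 without those covariates and about 1.0 with them. With no benefit at all, selection on baseline distress gives an OR without those covariates anywhere from 0.62 to 1.57.

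**The case against.** The strongest reply is that section 2-6 sets out to find predictors of severe anxiety, not to estimate the effect of support. For that aim, including PHQ-9 and anger is ordinary. This stands: the models are not misspecified for prediction. The fault lies in reading a predictor's coefficient as evidence for providing a service.

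The null result is also disclosed, in the Results, under Table 6 and in the Discussion. That is so, but the Discussion sets aside what it discloses. Nor does Table 5's p = 0.021 rescue the claim: Table 6 is presented as its correction, and Table 5 conditions on PHQ-9, anger and stress too.

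An extra model without PHQ-9 and anger would not identify the effect either. This is correct. Its value is to show how far the association depends on the adjustment.

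Four stronger readings are tempting, and the documents do not support them.

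- A reader might infer that the paper's whole call for services rests on this coefficient. Sections 5 and 6 do not cite it; they rest on distress, sleep, sedative use and stage.
- A reader might infer that patients selected themselves into support. The documents show only that it was not assigned. The figure below 15% is a cited national one, not this sample's.
- A reader might multiply 0.42 by 1 to 3 points and conclude that adjustment strips factors of 0.66 to 0.28. Those are conditional-scale figures and overstate the shift between models.
- A reader might set the shifts against OR 0.54. Reductions of one or two points (0.80, 0.63) are smaller than that effect; the comparison holds against 0.84, the corrected estimate.

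**Conclusion.** The point holds as a fault of interpretation confined to two places in the Discussion, with one plain reporting error. The OR of 0.54 is paired with a p-value that belongs to 0.84 (95% CI 0.43 to 1.63), and r = -0.07 is likewise compatible with zero. Neither the sign nor the size of these estimates identifies an effect of support, because support was not assigned and the adjusting measures may be its causes or its consequences.

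This does not show that support is ineffective or harmful: the data neither show nor exclude a benefit.

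The conversion to an odds ratio takes Table 6 as logistic, as its title says; the Results prose lists the same coefficients under linear regression, and this should be reconciled. The p-value for r assumes a simple correlation on all 500 patients. The PHQ-9 shifts are illustrations that depend on the assumed prevalence and point differences; they are not estimates of bias in this sample.

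**What to change.** 1. In the Discussion paragraph on support, replace OR 0.54 with 0.84 (95% CI 0.43 to 1.63) beside p = 0.606, delete the sentence on the direction of effect, and state that the data neither show nor exclude a benefit.
2. In the path-model paragraph, remove the inference from r = -0.07 or restate it as a hypothesis.
3. Define the support variable (type, timing, provider) as far as it was recorded, and give the numbers supported and unsupported with their PHQ-9 distributions.
4. Report support against severe anxiety twice: with stage and the collected demographics only, and with PHQ-9 and anger added. Label both as associations subject to selection and indication, and say that neither identifies a causal effect.
5. Let any call for services rest on the measured burden (mean PHQ-9 17.99, mean GAD-7 12.79 in Table 1), as sections 5 and 6 largely already do.

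The cost is one further model on existing data, a short descriptive table and a few sentences. The downside is that the paper loses an apparent argument that support is effective.

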**Table 2.** Spearman Correlation Matrix Among Study Variables

Variable	PHQ9_Total	GAD7_Total	Stress Level	Sleep Difficulty	Sleep Satisfaction	Total Cost

PHQ9_Total	1.00	0.79	0.66	0.85	0.49	-0.11
GAD7_Total	0.79	1.00	0.65	0.77	0.62	-0.10
Stress Level	0.66	0.65	1.00	0.85	0.55	-0.12
Sleep Difficulty	0.85	0.77	0.85	1.00	0.48	-0.08
Sleep Satisfaction	0.49	0.62	0.55	0.48	1.00	-0.09
Total Cost	-0.11	-0.10	-0.12	-0.08	-0.09	1.00

[figure not shown]
Spearman correlation coefficients between psychological outcomes and sleep-related variables are shown in **Table 2**. Strong positive correlations were observed between depression, anxiety, stress, and sleep difficulty.

**Table 3.** Kruskal–Wallis Test for Differences Across Cancer Stages

Variable	Chi-square (H)	df	P-value
Stress Level	31.092	3	<0.001
PHQ9_Total	14.762	3	0.002
GAD7_Total	19.705	3	<0.001

The Kruskal–Wallis test results (**Table 3**) indicate significant differences in depression, anxiety, and stress levels across cancer stages ( $P < 0.05$ ).

**Figure 1.** Chi-square (H) Values for Stress, Depression, and Anxiety

**Figure 1** shows the Chi-square (H) values for stress, depression, and anxiety. Stress exhibited the highest value (H = 31.09), followed by anxiety (H = 19.71) and depression (H = 14.76), all indicating significant differences across groups ( $P < 0.05$ ).

**Table 4.** Multiple Regression Analysis of Factors Associated with Depression, Anxiety, and Stress among Patients

Outcome	Predictor	B	T	P-value	VIF	R 
Depression (PHQ-9)	Use of Sedatives	4.842	10.817	<0.001	1.766	0.702
	Sleep Difficulty	4.52	11.221	<0.001	4.866	
	Sleep Satisfaction	0.364	2.01	0.045	1.021	
	Children	0.075	0.626	0.532	1.039	
	Total Cost	7.5E-5	2.209	0.028	1.022	

	Metastatic	-0.13	-0.408	0.684	1.048	
Anxiety (GAD7)	Use of Sedatives	4.064	12.807	<0.001	1.766	0.615
	Sleep-related Worry	1.521	6.193	<0.001	3.655	
	Sleep Satisfaction	0.539	1.886	0.060	4.866	
	Children	0.205	1.889	0.060	1.039	
	Total Cost	3.0E-5	1.246	0.213	1.022	
	Metastatic	0.203	0.896	0.371	1.048	
Stress Level	Use of Sedatives	1.856	29.413	<0.001	1.766	—
	Sleep-related Worry	0.149	3.048	0.002	3.655	
	Children	0.037	1.705	0.089	1.039	
	Metastatic	0.084	1.865	0.063	1.048	
	Total Cost	3.4E-6	0.711	0.477	1.022	

The results of the multiple regression analysis are summarized in **Table 4**. Use of sedatives and sleep-related worry were significant predictors of stress, depression, and anxiety scores.

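### The Discussion ranks depression and anger first among all predictors of severe anxiety, but no tabulated regression sets them against sleep or sedative use, and none of the linear models contains them

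*Combined protocol and SAP*

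**What the plan says.** Section 4 (Discussion) opens the ranking with "Among all predictors examined, depression" and continues that "anger emerged as the strongest independent predictors of severe anxiety in both logistic and linear regression models". It cites β = 0.42 for PHQ-9 and 2.08 for anger, both p < 0.001.

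Section 3 (Results) reports two logistic models for severe anxiety. Table 5, titled "Binary Logistic Regression – Predicting Severe Anxiety", has PHQ-9, anger, stress, psychological support and cancer stage. Of Table 6 the text says "This table presents the corrected logistic regression model for predicting severe anxiety"; it has PHQ-9, anger, psychological support and cancer stage.

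Sleep and sedative variables are analysed elsewhere in Section 3. The Table 2 row for anxiety reads "GAD7_Total 0.79 1.00 0.65 0.77 0.62 -0.10" (columns: PHQ-9, GAD-7, stress, sleep difficulty, sleep satisfaction, cost). The first row of the Table 4 anxiety block reads "Use of Sedatives 4.064 12.807 <0.001 1.766 0.615". The text under Table 4 says "Use of sedatives and sleep-related worry were significant predictors of stress, depression, and anxiety scores".

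Section 2-6 (Data Analysis) names binary logistic regression for severe anxiety. It gives no list of candidate predictors and no rule for choosing them.

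**The concern.** To call a predictor the strongest independent one among all those examined, the candidates must have been in the same model, or at least compared on a common scale. Here the candidates were split. Depression and anger were entered for severe anxiety; sleep-related worry, sleep satisfaction and sedative use were entered for the GAD-7 total. The sentence then ranks across the split.

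The mention of linear models adds a second source of support that the tables do not show.

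What depends on this is fairly narrow. Soon after the ranking, the Discussion infers that screening tools should cover anger. That recommendation rests on a predictor that no tabulated regression adjusts for sleep disturbance or sedative use, although both are reported as closely tied to distress.

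**Working it through.** **1. Reproducing Table 6.** With z = b/SE from the rounded entries:
- PHQ-9: 0.42/0.06 = 7.00 (printed 6.92)
- Anger: 2.08/0.48 = 4.33 (4.36)
- Support: -0.18/0.34 = -0.53 (-0.52)
- Stage: 0.92/0.29 = 3.17 (3.20)

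The table is internally consistent within rounding. By |z|, PHQ-9 and anger are first and second among its four terms.

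**2. Which terms met in which regression (as printed).**

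| Model | Outcome | PHQ-9 | Anger | Sleep terms | Sedatives |
|---|---|---|---|---|---|
| Table 5, logistic | Severe anxiety | yes | yes | none | no |
| Table 6, logistic | Severe anxiety | yes | yes | none | no |
| Table 4, linear | GAD-7 total | no | no | worry, satisfaction | yes |

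No row has both groups. Sleep difficulty has no row in the Table 4 anxiety block; under that name it meets GAD-7 only as a bivariate correlation in Table 2.

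**3. The linear claim.** Section 3 lists 0.42, 2.08 and 0.92, with stage p = 0.0014 and support p = 0.606, as multivariate linear results. All of these figures are the Table 6 entries, and Table 6 is logistic.

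**4. Do 0.42 and 2.08 rank strength?** They are log-odds per PHQ-9 point and per unit of anger, and the coding of anger is not stated. Using Table 1 SDs, and assuming stage in Table 6 has the Table 1 spread:
- PHQ-9: 0.42 × 6.11 = 2.57 per SD
- Stage: 0.92 × 1.09 = 1.00 per SD
- Anger, if coded 0/1 (assumption): at most 2.08 × 0.5 = 1.04 per SD; at 20% prevalence, 2.08 × 0.4 = 0.83

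Under that assumption anger is about level with stage or below it. If anger is a multi-level score, its effect per SD could be larger.

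**5. Strength of the omitted terms in Table 4 (GAD-7).** Partial r = t/√(t² + df), with df = 500 - 6 - 1 = 493:
- Sedatives: 12.807/√(164.0 + 493) = 0.50
- Sleep-related worry: 6.193/√(38.4 + 493) = 0.27
- Every other term: about 0.08 or less

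**6. Approximate joint check for PHQ-9.** Spearman coefficients are treated as ordinary correlations and the outcome is continuous GAD-7. Inputs from Table 2: PHQ-9 with GAD-7 0.79, sleep difficulty with GAD-7 0.77, PHQ-9 with sleep difficulty 0.85.
- PHQ-9 alone: β = 0.79, R² = 0.79² = 0.624
- PHQ-9 jointly: (0.79 - 0.85 × 0.77)/(1 - 0.85²) = 0.1355/0.2775 = 0.488
- Sleep difficulty jointly: (0.77 - 0.85 × 0.79)/0.2775 = 0.0985/0.2775 = 0.355
- Joint R² = 0.488 × 0.79 + 0.355 × 0.77 = 0.659
- With n = 500, t = 9.8 for PHQ-9 and 7.1 for sleep difficulty

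The PHQ-9 coefficient falls by (0.79 - 0.488)/0.79 = 38% and remains the larger of the two. Anger and sedatives are not in Table 2, so neither can be added.

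**The case against.** - **The order within the fitted models is consistent.** PHQ-9 and anger lead by z in Table 6 (6.92 and 4.36, against 3.20 for stage). They also lead in Table 5, where z recovered from the intervals is 3.90 and 3.18 against at most 2.38. This stands. It supports a claim about those models, not about everything examined, and z measures evidence rather than size of effect.
- **PHQ-9 may well come first.** It is the top GAD-7 correlate in Table 2 (0.79) and stays ahead of sleep difficulty in step 6. This also stands. A reader might infer that the sleep and sedative variables are the stronger correlates of anxiety. Table 2 does not show that: sleep difficulty is second at 0.77, and sedatives are absent. Sedatives and worry lead in Table 4, but PHQ-9 and anger were not entered there.
- **Sleep is not neglected.** A reader might infer that the ranking pushes sleep aside. The Discussion, Clinical Implications and Conclusion all give sleep a prominent place, so that does not hold.
- **The path model.** The Discussion says it includes anger alongside sleep disturbance. However, it is described as conceptual, the text gives no coefficient for anger, and it is not one of the regressions the sentence relies on. Its figure was not available for this review.
- **A possible label slip.** In the Table 4 anxiety block, sleep satisfaction carries VIF 4.866, the value printed for sleep difficulty in the depression block. If the row is really sleep difficulty, step 2 is unchanged: PHQ-9 and anger are still absent from that model.
- **No planned analysis was skipped.** Section 2-6 lists no predictors, so a joint model would be an addition. That is correct, and it is why rewording is sufficient.

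**Conclusion.** The ranking across all predictors examined is unsupported by the regressions reported, and the reference to linear models has no tabulated model behind it. Both conclusions follow from reading Tables 4, 5 and 6 side by side and need no assumption beyond taking the row labels as printed.

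The numerical size is only indicative. On continuous GAD-7, with rank correlations used as inputs, PHQ-9 loses about 38% of its standardised coefficient when sleep difficulty enters, and still exceeds it (0.49 against 0.355). A reader might infer that the ranking is wrong. The documents do not show that: for PHQ-9 it is untested, and for anger the tables allow no check in either direction. The severe-anxiety model itself cannot be refitted from the published figures.

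The practical consequence is limited mainly to the anger-screening inference.

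**What to change.** **Minimum change, wording only.**
- Limit the Discussion sentence to the four predictors entered in Table 6.
- Delete the reference to linear models, and relabel the matching list in Section 3 as logistic.
- State that the anger finding, and the screening suggestion drawn from it, are not adjusted for sleep or sedative use.

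**To keep the broader ranking.** Fit one logistic model for severe anxiety with PHQ-9, anger, stage, psychological support, sleep difficulty or sleep-related worry, and sedative use. State how anger is coded, and report effects per SD with confidence intervals and VIFs. Describe it as an added analysis.

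**Cost.** The wording change costs nothing in data or time; the model is one further fit on data already held. Its drawback is collinearity. PHQ-9 and sleep difficulty correlate at 0.85, a pairwise VIF of 1/(1 - 0.85²) = 3.6. Section 3 reports sedatives at r > 0.90 with distress scores; if that includes PHQ-9, the pairwise VIF exceeds 1/(1 - 0.90²) = 5.3. Intervals will widen and may not separate the predictors, in which case the text should say so. The number of patients with severe anxiety is not reported, so the precision of the joint model cannot be forecast from the document.
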